12.6 Reporting Procedures for All Adverse Events

All AEs* (including SAEs) occurring during the study will be reported on the running logs in the AE section of the CRF. This includes all events from the time following screening (Visit 1) to post study follow-up (Visit 13 for patients entering the OLE and Visit 6 for those patients that are not entering the OLE). whether or not attributed to IMP and observed by the investigator or patient.

*For the patient's expected seizure types, these do not routinely require documentation as AEs. However, any worsening, including change in the pattern or severity of seizures must be documented as an AE. Any AE which meets SAE criteria should still be reported as a SAE.

The following information will need to be provided for all AEs:

A) Adverse Event (Diagnosis or Syndrome if known, or Signs and Symptoms)

Where the investigator cannot determine a diagnosis, signs or symptoms should be recorded on the AE section of the CRF. Once a diagnosis has been determined the AE section of CRF must be updated to reflect the diagnosis in replacement of the original symptoms. In circumstances where only a provisional diagnosis is possible (working diagnosis), the CRF must be updated to reflect the provisional diagnosis in replacement of the original symptoms. In some circumstances it may be relevant for the investigator to include the symptoms alongside the diagnosis in the verbatim event description. However, the diagnosis (full or provisional) should be clearly stated e.g., fever and malaise due to a respiratory tract infection.

B) Adverse Event Start Date and Stop Date

The start and stop dates of the event must be provided. All AEs require these fields to be completed in full. Partial dates or missing dates are not normally acceptable and significant effort must be undertaken to obtain any unknown information. If a precise date is not known an estimated date should be provided instead. When a complete date cannot be given then record as much information as possible (i.e., month and year or in exceptional circumstances just year). When the actual start date becomes known the CRF must be updated to replace the previously recorded date.

C) Outcome

The outcome of the event must be recorded accurately and classified into one for the following categories:

- Recovered.
- Recovered with sequelae.
- Continuing.
- Patient died.

D) Severity

When describing the severity of an AE the terms mild, moderate, or severe should be used. Clinical judgment should be used when determining which severity applies to any AE.

If the severity of an AE fluctuates day-to-day, for example, a headache or constipation, the change in severity should not be recorded each time, instead only the worst observed severity should be recorded with AE start and stop dates relating to the overall event duration regardless of severity.

A severe AE is not the same as a SAE. For example, a patient may have severe vomiting but the event does not result in any of the SAE criteria above. Therefore it should not be classed as serious.

E) Causality

See [Section 12.5](#) above.

F) Action Taken with Study Medication

This question refers to the action taken with the IMP due to an AE. The action with the IMP must be classed as:

- None.
- Dose reduced temporarily.
- Dose reduced.
- Study medication interrupted.
- Study medication stopped.

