who were taking GWP42003-P during the blinded period will maintain their 20 mg/kg/day dose throughout the transition from the blinded period into the OLE period and patients who received placebo during the blinded period up-titrate slowly to the 20 mg/kg/day dose in the OLE period. After this has taken place after Visit 5, the maintenance dose of GWP42003-P may be adjusted up or down at the discretion of the investigator to a maximum of 30 mg/kg/day (no minimum).

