12. ADVERSE EVENT REPORTING

12.1 Definitions

12.1.1 Adverse Event

For the purposes of this study an AE is defined as:

Any new unfavorable/unintended signs/symptoms (including abnormal laboratory findings), or diagnosis or worsening of a pre-existing condition, which is present following screening (Visit 1) throughout the study and up to the post treatment, safety follow-up visit (28 days after last dose of IMP), which may or may not be considered to be related to the IMP. Any event that is the result of a study procedure must be recorded as an AE.

Surgical/Investigational procedures are not AEs. The medical reason for the procedure is the AE. Elective hospitalizations for pre-study existing conditions or elective procedures are not AEs. The exception may be if the patient has an AE during hospitalization which prolongs their scheduled hospital stay in which case it would be considered a SAE (refer to [Section 12.2](#)).

If reporting a fatal event, the SAE term should be the underlying cause of the death (e.g., disease or medical condition leading to death).

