12.5 Causality Assessment

Causality assessment is required for all AEs and SAEs. Causality assessment must only be assigned by the investigator. All cases judged as having a reasonable suspected causal relationship to the study medication must be reported as such. The expression "*reasonable causal relationship*" is meant to convey in general that there are facts (evidence) or arguments to suggest a causal relationship.

The following question which must be answered by the investigator for all AEs is used to capture the reasonable causal relationship of an event to the study medication:

"In your opinion is there a plausible relationship to the study medication?" The answer is "yes" or "no".

Events that start before the first dose of study medication (pre-treatment) should be considered as not causally related. Where a pre-treatment event worsens in severity following the first dose of study medication, a new event record should be entered into the CRF.

Considering the explanation given above, investigators are strongly encouraged to express their opinion on what the cause of an AE might be. For individual patients, the investigator is usually in the best position to assess the underlying suspected cause of an AE. For all AEs and especially SAEs, it is important that the investigator assess not only the possible role of the study medication but also competing etiological factors as the underlying cause. Factors for consideration may include:

- Medical history.
- Lack of efficacy/worsening of treated condition.
- Concomitant or previous treatment.

- Withdrawal of study medication.
- Protocol-related procedure.

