13.6.4.2 Adverse Events

AEs will be coded according to the Medical Dictionary for Regulatory Activities dictionary.

A treatment emergent AE is one that started, or worsened in severity or seriousness, following the first dose of IMP.

Descriptive presentations of treatment emergent AEs will be given by preferred term and system organ class for the safety analysis set. The number of patients reporting at least one AE will be provided. Summaries will be provided for each phase of the study separately.

The following summaries will be produced:

- All-causality AEs.
- Treatment related AEs.
- All-causality AEs by severity.
- All-causality serious AEs.
- Treatment related serious AEs.
- AEs reported as leading to permanent cessation of study treatment.
- Fatal AEs.

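### An AE that fluctuates across the first open-label dose keeps one record with its worst grade, so an open-label grade can appear in the blinded-phase severity tables, including under placebo

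*Protocol*

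**What the plan says.** Four parts of the protocol bear on this.

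- **Recording of severity (section 12.6, item D).** The rule is conditional: "If the severity of an AE fluctuates day-to-day, for example, a headache or constipation", the individual changes are not entered; "instead only the worst observed severity should be recorded with AE start and stop dates relating to the overall event duration regardless of severity".
- **Opening a new record (section 12.5).** "Where a pre-treatment event worsens in severity following the first dose of study medication, a new event record should be entered into the CRF". This is the only place where sites are told to split an event because its severity changed after a treatment step.
- **Analysis (section 13.6.4.2).** An event counts as treatment emergent if it began, or became more severe or more serious, after the first IMP dose. The Definition of Terms counts placebo as IMP. All-causality AEs by severity are among the listed tables, and "Summaries will be provided for each phase of the study separately".
- **Treatment change at the phase boundary (section 8.1.2).** On entering the extension, "patients who received placebo during the blinded period up-titrate slowly to the 20 mg/kg/day dose in the OLE period". Table 8.1.2-1 starts this on Day 34.

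Two other provisions mention worsening. For expected seizure types, section 12.6 says "However, any worsening, including change in the pattern or severity of seizures must be documented as an AE". The AE definition in section 12.1.1 includes "or diagnosis or worsening of a pre-existing condition, which is present following screening (Visit 1) throughout the study".

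**The concern.** Section 12.5 recognises that worsening after a new exposure needs its own record, and it applies that to the first dose of study medication. For a placebo patient who enters the extension, the first exposure to GWP42003-P comes later, at the first open-label dose. Protocol amendment 3 acknowledged this: it added a clinic observation period at that dose because it may be the patient's first exposure to the drug. The AE recording rules were not changed to match.

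Comparison of safety with placebo is a secondary endpoint (section 4.1.2), and the blinded phase is the only randomised comparison available for it. If a grade reached on open-label drug is carried back into that phase, the severity table no longer describes what happened under the randomised treatment. The loss occurs at data capture. A SAP can choose how to assign events to phases, but it cannot recover from the AE record a grade and a date that sites were told not to enter.

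**Working it through.** The protocol has no figure to reproduce on this point. The check sets the recording rules against the tables they feed, followed by simple arithmetic for scale.

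**Step 1: what the record holds.** Take an illustrative placebo patient who enters the extension. A headache starts on Day 20 and varies between mild and moderate from day to day until the first open-label dose. It continues, and varies between mild and severe afterwards. Under section 12.6 D this is one record: start Day 20, severity severe, stop date when the whole event ends. Section 12.5 does not split it, because the headache began after the first dose of study medication. The moderate grade and the date on which severe was first reached are not in the record.

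**Step 2: what the by-phase severity table can show.** The protocol gives no rule for assigning an event that spans the first open-label dose. The two ordinary choices give:

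| Assignment | Blinded phase (placebo) | Extension |
|---|---|---|
| By start date | Severe | No entry |
| To every phase in which it is ongoing | Severe | Severe |
| What actually occurred | Moderate | Severe |

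Under both choices the open-label grade enters the blinded column. The true row cannot be built from the single record under any assignment rule, because it needs the grade before Day 34. Loss of the event from the extension occurs only under assignment by start date.

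**Step 3: do the other worsening provisions prevent this?** The seizure provision in 12.6 covers expected seizure types, not a headache. The definition in 12.1.1 makes worsening of a pre-existing condition an AE, but it does not tell sites to open a second record when an AE already on the log worsens after Day 34.

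**Step 4: does the planned interim analysis prevent this?** Section 13.2 places an analysis at the end of the double-blind phase. Patients enrolled early may already be in the extension by then, and their single records may already carry an open-label grade.

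**Step 5: scale.** Inputs: 20 patients (section 13.1) and 4:1 allocation (section 7.2).

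- Placebo: 20 × 1/5 = 4 patients; one event is 1/4 = 25 percentage points.
- GWP42003-P: 20 × 4/5 = 16 patients; one event is 1/16 = 6.25 percentage points.

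**Step 6: which arm is affected.** The same recording applies to the active arm. Those patients continue on open-label drug for up to a year, at up to 30 mg/kg/day after Visit 5 (section 8.1.2). A later worse grade in a fluctuating event that began in the blinded phase would be carried back into the blinded active column in the same way.

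**The case against.** The strongest case on the other side is that the protocol does not state the outcome and the SAP may deal with it. Several parts of that case stand.

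- A reader might infer that the protocol itself tabulates such events in the blinded phase and leaves them out of the extension. It does not say so. Phase assignment is properly left to the SAP, which was not examined here, and omission from the extension depends on using the start date.
- A reader might take the single-record rule to cover any worsening. It covers day-to-day fluctuation. A headache that is steadily mild and then steadily severe after the first open-label dose is not clearly caught; for sustained worsening the protocol neither requires nor forbids a new record.
- A reader might conclude that the comparison is biased toward no difference, because placebo patients cross to active drug. The documents do not support a direction. Carry-back in the active arm would work the other way, and no frequencies are given.
- The 25 and 6.25 points are properties of any single event in groups of 4 and 16. They do not estimate how often this would happen. The affected set is narrow: the event must be ongoing at the first open-label dose, in a patient who enters the extension, and must then worsen. The analysis is also declared descriptive (section 13.1).
- Daily diaries (section 9.1.13) and AE reviews at Visit 4 and at two weeks may hold the timing at source. Worsening to a serious event also goes through SAE reporting (section 12.3).

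These points limit the claim but do not remove it. The diary and visit notes are not the AE record that feeds the tables. Section 12.3 has the AE section of the CRF updated for new SAE information and does not call for a second record. Neither ordinary phase-assignment rule yields the correct blinded-phase grade.

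**Conclusion.** The point holds in a limited form. For an AE whose severity fluctuates from day to day, which starts in the blinded phase and worsens in the extension, the stated recording rule discards the blinded-phase grade and the worsening date. The blinded-phase severity table can then show an open-label grade, including under placebo, whether events are assigned by start date or by phases in which they are ongoing. If they are assigned by start date, the extension table also misses the event. For sustained worsening the instruction is silent, so sites may record it differently.

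One such event is 25 points of the placebo column, or 6.25 points of the active column. This assumes that 20 patients are enrolled and split exactly 16 and 4. The number of such events is unknown, and the net direction of bias is uncertain because both arms can be affected. The change should be made, since a stated rule produces a wrong entry that analysis of that record cannot repair. With descriptive safety analyses, it does not threaten the trial's main conclusions.

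**What to change.** Extend the rule in section 12.5 to the phase boundary. An AE ongoing at the first open-label dose that afterwards worsens in severity or seriousness, whether by fluctuation or in a sustained way, gets a new record that starts on the date of worsening and is counted in the extension. The first record keeps the worst severity observed before the first open-label dose, and the blinded-phase tables use that grade. State in section 12.6 D that this split is exempt from the single-record rule, and repeat the instruction in the CRF completion guidance.

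The cost is about one sentence in each of the two sections and a few extra AE records for patients who enter the extension. The event count rises slightly, because one continuing condition can then contribute a record to each phase. No treatment or clinical rule changes.

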12.7 Follow up Procedures for Adverse Events

The investigator may be asked to provide follow-up information to the GW PVD for any AEs reported.

AEs considered related to the IMP by the investigator or the sponsor should be followed up until resolution or the event is considered stable.

It will be left to the investigator's clinical judgment whether or not an AE is of sufficient severity to require the patient's removal from treatment. A patient may also voluntarily withdraw from treatment due to what he or she perceives as an intolerable

AE, further details of withdrawal are presented in [Section 10](#). If either of these occurs, the patient must undergo an end of treatment assessment and be given appropriate care under medical supervision until symptoms cease or the condition becomes stable.

12.8 Potential Cases of Drug Induced Liver Injury

All investigational sites are required to submit to the GW PVD the laboratory results for any patient after randomization that meet the criteria for the selected laboratory parameters as follows:

- ALT or AST $> 3 \times \text{ULN}$ **and** (TBL $> 2 \times \text{ULN}$ **or** INR > 1.5).
- ALT or AST $> 3 \times \text{ULN}$ with the appearance of fatigue, nausea, vomiting, right upper quadrant pain or tenderness, fever, rash, and/or eosinophilia ($> 5\%$).
- ALT or AST $> 8 \times \text{ULN}$.
- ALT or AST $> 5 \times \text{ULN}$ for more than two weeks.

These reports must be sent to the GW PVD using the same fax number for SAE reporting within 24 hours of becoming aware of the results. In addition, please send a copy of the patient's baseline laboratory results with all reports to GW PVD.

Abnormal values in AST and/or ALT concurrent with abnormal elevations in TBL that meet the criteria outlined above are considered potential cases of drug-induced liver injury and will be considered as protocol defined criteria for withdrawal and important medical events. The investigator will arrange for the patient to return to the investigational site as soon as possible (within 24 hours of notice of abnormal results) for repeat assessment of ALT, AST, TBL, alkaline phosphatase and gamma-glutamyl transferase levels, detailed history and physical examination. Patients should be followed until all abnormalities have normalized (in the investigator's opinion) or returned to the baseline state.

Elevations in ALT or AST $> 3 \times \text{ULN}$ or TBL $> 2 \times \text{ULN}$ alone are not considered potential cases of drug-induced liver injury, but will be followed as detailed above, within 72 hours' notice of abnormal results. If the participant cannot return to the investigational center, repeat assessments may be done at a local laboratory and the results sent to GW PVD.

12.9 Notification of Safety Information to Investigators, Regulatory Authorities and Ethics Committees.

In accordance with the EU Clinical Trials Directive³⁵, relevant parts of the FDA Code of Federal Regulations and any national regulations, GW will inform investigators,

regulatory authorities and relevant IRB/ECs of all relevant safety information. This will include the reporting of relevant SAEs and all Suspected Unexpected Serious Adverse Drug Reactions (SUSARs).

This information will be provided through three sources:

- Investigator Brochure³⁶: a compilation of the clinical and non-clinical safety data available on the IMP that is relevant to the study on the IMP in human participants. The IB is updated annually.
- Development Core Safety Information: this document actually forms the Safety Section of the IB³⁶, or is updated as an appendix of the IB³⁶. This document is revised if necessary, when new important safety information becomes available (potentially up to a few times a year).
- Council for International Organizations of Medical Sciences (CIOMS) reports: these reports are issued every time a SUSAR is reported to GW. They provide information on individual case reports and are sent to all the regulatory authorities, the relevant central IRB/ECs which have approved the study and investigators. As required, the investigator should notify their regional IRB/EC of SAEs or SUSARs occurring at their site and other AE reports, i.e., CIOMS reports and any additional safety documentation received from GW, in accordance with local procedures.

In the USA, investigators are normally required to promptly report to their IRBs all unanticipated problems involving risks to human patients, or others, including AEs that should be considered unanticipated problems. Based on current FDA guidance³² the following clarification is provided in determining what constitutes an unanticipated problem:

In general, an AE observed during the conduct of a study should be considered an unanticipated problem involving risk to human patients, and reported to the IRB, *only* if it were unexpected, serious, and would have implications for the conduct of the study (e.g., requiring a significant, and usually safety-related, change in the protocol such as revising inclusion/exclusion criteria or including a new monitoring requirement, informed consent, or IB). An individual AE occurrence *ordinarily* does not meet these criteria because, as an isolated event, its implications for the study cannot be understood.

The FDA guidance³⁷ states that, accordingly, to satisfy the investigator's obligation to notify the IRB of unanticipated problems, any investigators participating in a multicenter study may rely on the sponsor's assessment and provide to the IRB a report of the unanticipated problem prepared by the sponsor.

GW will inform investigators (regulatory authorities and applicable IRB/EC's) of any safety issues or case reports that are considered to be unanticipated and provide such

reports as mentioned above. It should be noted that a single SUSAR report notified to investigators in the study does not necessarily constitute an unanticipated problem unless identified by GW in the submission cover letter.

As a minimum, the recipient will be sent all of the above and relevant updates between the period from ethics approval and final database lock.

13. STATISTICAL CONSIDERATIONS

A statistical analysis plan (SAP) will be produced prior to the database lock and analysis of the study. Any deviations from the original SAP will be described in the final clinical study report.

13.1 Sample Size, Power and Significance Levels

A total of 20 patients will be enrolled in this study. There is no formal sample size: Calculation and analysis is descriptive only.

13.2 Interim Analysis

An interim analysis will be conducted at the end of the Double Blind phase of the study and may also be considered during the OLE phase, if long term data is required to support New Drug Application/Marketing Authorization Application submissions.

13.3 Analysis Sets

13.3.1 Safety Set

All subjects who are treated and receive at least one dose of IMP will be included.

The Safety set is the primary analysis set for all safety endpoints.

13.3.2 Pharmacokinetic Analysis Set

All subjects who are treated and receive at least one dose of IMP and who provide some on-treatment data will be included.

The PK analysis set is the primary analysis set for all PK endpoints.

